11.1.5 Hematologic and Biochemical Toxicity Evaluation

Blood samples for evaluation of hematologic and biochemical toxicity, and urine samples for urinalysis will be obtained from each participant on Day -21 to -1 (screening period) and again on Day 0 prior to device placement, if screening samples were taken more than 3 days prior, then Days 3, and 42. If deemed necessary, other toxicity tests (to be determined) may be performed with these samples as well.

The samples will be prepared and shipped according to specifications provided by the testing laboratory at the investigator's site where the tests will be performed. The toxicity evaluation tests will include hematologic testing, serum biochemistry testing, and urinalysis as indicated in the table below.

Safety Laboratory Tests to be Conducted

Hematology (Complete Blood Count)	White Blood Count	Mean Corpuscular Hemoglobin Concentration
	Red Blood Count	RDW
	Hemoglobin	Platelet count
	Hematocrit	Prothrombin Time (PT)
	Mean Corpuscular Volume	Partial Thromboplastin Time (PTT)
	Mean Corpuscular Hemoglobin	
Blood Chemistry	Sodium	Creatinine
	Potassium	Calcium
	Chloride	Alanine Aminotransferase (ALT)
	Bicarbonate	Alkaline Phosphatase
	Glucose	Bilirubin
	Blood Urea Nitrogen (BUN)	
Urinalysis	Color	Nitrite
	Specific Gravity	Leukocyte esterase
	pH	Turbidity
	Protein	Crystals
	Glucose	Bacteria
	Ketones	WBC
	Bilirubin	RBC
	Blood	

Laboratory values that are outside the institutional range for normal lab values (Appendix A of this document) will be recorded as AEs only if they are deemed clinically significant in the judgment of the Investigator. In order to assign clinical significance of abnormal lab values, the Investigator will use as a guide the institutional lab range of normal values.

11.2 Osteoinduction

Radiographic and CT scan assessment for osteoinduction at the site of the experimental device will be performed according to protocol for all subjects, unless the investigator determines that it is not in the best interest of the subject to continue with imaging.

11.2.1 Osteoinduction Evaluation

The primary outcome for osteoinduction is assessed by CT analysis.

12. STUDY MEDICATION

12.1 Product Description

The B-247 Cranial Bone Graft Implant is an experimental device which consists of plasmid DNA (pln.247-pBI, 200 µg/ml of implant volume) for transient expression of human perlecan domain 1 with 100 µg/ml rhBMP-2 in a gelatin/tricalcium phosphate scaffold for cranial bone regeneration. The product is provided as a pliable solid single-phase unit consisting of 80% bioactivated tricalcium phosphate (TCP) crystals 200-600 µm particle size, evenly distributed within a 20% cross-linked gelatin polymer. The implant is bioactivated by incorporating plasmid DNA lipoplexes and rhBMP-2 in 1% sucrose excipient, then lyophilizing the loaded implant to a final concentration of 200 µg/ml of implant of pln.247-pBI plasmid and 100 µg/ml of implant of rhBMP-2. Plasmid lipoplexes are derived from incubating pln.247-pBI plasmid with Lipofectamine 2000 in a

2:1 ratio for 30 minutes. Sucrose, plasmid, rhBMP-2, Lipofectamine 2000, TCP crystals, and gelatin are each manufactured separately according to cGMP and combined under sterile conditions in a clean room.

12.2 Dosing

The device will deliver 200 $\mu\text{g}/\text{ml}$ of graft material of the B-247 plasmid, and 100 $\mu\text{g}/\text{ml}$ of graft material of the rhBMP-2. The amount of graft material that is required to fill the bone defect should be applied. The total dose to the participant will vary depending on the amount of the device required to fill the bone defect. However, the dose per volume of graft material will remain constant.

12.3 Labeling

All study devices will be provided by Agenta and labeled with an investigational product label. Examples of the investigational product label are reproduced below:

Cranial B-247 Investigational Bone Graft Implant:

B-247 Investigational Bone Graft

100 $\mu\text{g}/\text{ml}$ rhBMP-2

200 $\mu\text{g}/\text{ml}$ B-247 DNA plasmid

vol: 28 ml

Store at $4^{\circ}\text{C} \pm 3^{\circ}\text{C}$

Caution: Investigational Device – Limited by US Law to investigational use.

Agenta Biotechnologies, Inc.

12.4 Packaging

The formulated, sterile drug product will be packaged in a sealed wrapper with label affixed. Upon use, the wrapper will be torn or cut open and the semi-solid experimental bone graft device will be dropped onto the surgical field for shaping and surgical placement.

12.5 Storage, Issue, and Return of Study Medication

All study device and placebo will be provided by Agenta and labeled with an investigational product label, as described in Section 12.3. Study device will be shipped to the study site pharmacy on ice and must be stored in a secured, monitored alarmed refrigerator at $4 \pm 3^{\circ}\text{C}$. The study product temperature will be continuously monitored and any deviations from the acceptable range for the study product storage temperature will be noted by the pharmacist including the temperature, date and time.

The site pharmacist will maintain documentation showing receipt, shipment, and disposition of investigational device. This documentation will include the investigator's name, and product code/ lot number for each shipment. An investigational product dispensing and reconciliation form will be maintained for all study devices.

When the site pharmacist is notified that the subject is available for device placement, the unblinded pharmacist will withdraw a device package from the refrigerator. Unused product should be returned to Agenta with the appropriate documentation at the time of study close-out.

Once the investigational device accountability has been verified at the end of the study, all unused graft material must be returned to Agenta with the appropriate documentation.

13. STATISTICAL EVALUATION

13.1 Sample Size Calculation

The goal of the safety evaluation for this study is to identify safety concerns associated with device administration. Sample size calculations for safety are expressed in terms of the ability to detect rare events [e.g. serious adverse events (SAEs)]. The ability of the study to identify serious adverse experiences can be expressed by the maximum true rate of events that would be unlikely to be observed and the minimum true rate of events that would very likely be observed. Specifically, for a group size of 10, there is a 90% chance of observing at least 1 serious adverse experience if the true rate of such an event is at least 21%; there is a 90% chance that at least 1 SAE would not be observed if the true rate was no more than 1%.

Probabilities of observing 0, or 2 or more, SAEs among a group of 10 subjects are presented in the following table for a range of possible true event rates. These calculations provide a more complete picture of the sensitivity of this study design to identify potential safety problems with the experimental device. Note that the planned group size for the study will be 12, i.e., 2 subjects more than the sample size calculations illustrated here.

Probability (%) of Response for Different Safety Scenarios

True Event Rate (%)	Pr (0/10)	Pr (2+/10)
1.0	90.4	0.4
3.4	70.0	4.6
5.0	59.9	8.6
10.0	34.9	26.4
20.0	10.7	62.4
30.0	2.8	85.1
40.0	0.6	95.4
50.0	<0.1	98.9
60.0	<0.1	99.8

13.1.1 Responsibility for the Analysis

The principal investigator will conduct the safety evaluations at the study site on Days 0, 3, 7, 42, 180, and 360. The SRC will review safety data for specific cohorts of subjects at protocol-specified intervals.

A full statistical analysis will be performed under the control of Agenta after all Day 180 data is received in-house, and again after all Day 360 data is received in -house. The study statistician will be responsible for completing the statistical analysis of all safety and efficacy data.

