6. OBJECTIVES

6.1 Primary Objective

The primary objective is to evaluate the safety of the B-247 Cranial Bone Graft Implant when administered to adults with cranial bone defects in medical need of repair.

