7. STUDY DESIGN

7.1 Study Overview

This is a single center, unblinded, safety and efficacy study.

A total of 12 subjects will be enrolled.

All 12 subjects will receive the B-247 Cranial Bone Graft Implant.

Enrollment will begin with 3 subjects enrolled at a rate of no more than one subject per week. The second, and third subjects will only be treated with the experimental device if stopping rules (see Section 14.3) are not met and other safety concerns are absent. Following review of Day 7 safety data for each of the first 3 subjects, the SRC will determine whether to open enrollment to the remaining 9 subjects or to discontinue enrollment. The SRC will review the occurrence of AEs weekly, with 24 hour reporting for SAEs. Stopping rules are described in full in Section 14.3.

Safety will be assessed in all participants. Each participant will be requested to record solicited AEs daily for 2 years after their device placement using study diary cards. Additionally, unsolicited adverse events will be collected immediately following surgical device placement through two years via telephone contacts and at clinic visits. Serious adverse events (SAEs) will be collected throughout the 2 year period of safety surveillance.

Safety evaluation will include hematologic and biochemical toxicity evaluation.

Blood and urine samples will be collected at screening (Day -21 to -1), on Day 0 prior to administration of the device, and again on Days 7, and 42 to measure the effects of device on blood chemistry, urinalysis, and hematology. The urine and blood samples obtained on Day 0 will be used for the baseline comparison.

Subjects will be asked to undergo a physical examination at screening (Day -21 to -1) and a physical assessment including vital signs, lymph node exam, and symptom directed exams at all clinic visits following enrollment (Days 0, 3, 7, 42, 180, and 1 year).

Telephone contacts will occur on the first two days after surgery (Days 1, 2) for study staff follow-up on possible adverse events. In addition, telephone contacts will be made after two years to document the occurrence of SAEs and the resolution of AEs ongoing at the one-year visit.

The overall safety assessment of the device will be based on the incidence of local and systemic reactogenicity, the incidence of changes to laboratory parameters relative to baseline values, and solicited and unsolicited adverse events.

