- e. Obtain blood samples (10 mL + 5 mL) and urine sample for clinical laboratory assessments.
- f. Obtain blood sample (4 mL) for PT and PTT tests.
- g. Collect and discuss diary card / distribute new diary card.
- h. Record AEs and SAEs.
- i. Set up appointment for Visit 4 (Day 42).

Visit 4 (Day 42)

- a. Confirm that the subject wishes to remain in the trial.
- b. Obtain interim medical history.
- c. Review diary card with subject.
- d. Record concomitant medication.
- e. Perform physical assessment (vital signs, lymph node exam, and symptom directed exam).
- f. Obtain blood samples (10 mL + 5 mL) and urine sample for clinical laboratory assessments.
- g. Obtain blood sample (4 mL) for PT and PTT tests.
- h. Record AEs and SAEs.
- i. Obtain radiographs and CT images of experimentally treated cranial defect.
- j. Set up appointment for Visit 5 (Day 180).

Visit 5 (Day 180)

- a. Confirm that the subject wishes to remain in the trial.
- b. Obtain interim medical history.
- c. Review diary card with subject.
- d. Record concomitant medication.
- e. Perform physical assessment (vital signs, lymph node exam, and symptom directed exam).
- f. Record AEs and SAEs.
- g. Obtain CT images of experimentally treated cranial defect.
- h. Set up appointment for Visit 6 (Day 360).

Visit 6 (Day 360)

- a. Confirm that the subject wishes to remain in the trial.
- b. Obtain interim medical history.
- c. Review diary card with subject.
- d. Record concomitant medication.
- e. Perform physical assessment (vital signs, lymph node exam, and symptom directed exam).
- f. Record AEs and SAEs.
- g. Obtain CT images of experimentally treated cranial defect.
- h. Set up appointment for Contact 3 (Day 730).

Telephone Follow-up (Day 730)

Study personnel (study coordinator or other personnel assigned by the investigator) will contact the participant to collect information on ongoing, previously recorded adverse events and new or ongoing SAEs. Reminder postcards will be mailed to each participant approximately one month prior to this contact. Study personnel will contact the participant by telephone approximately two weeks in advance of the follow-up target date to schedule a time for the telephone contact. During the telephone conversation, study personnel will collect interim medical history as well as update contact information.

Contact 3 (Day 730)

- a. Confirm that the subject wishes to remain in the trial.
- b. Obtain interim medical history.
- c. Record AEs and SAEs.

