11.1.3 Unsolicited Adverse Events

All AEs and SAEs, including any condition that, according to the subject, represents a change in health status, and that occurs after the first administration of the study agent on Day 0 until the follow-up assessment at Contact #3 (Day 720) will be recorded. This information will be actively surveyed at every telephone contact or site visit with the subject during the period between Visit 1 and Contact #3. All SAEs that occur after the first administration of the study agent until the 2 year follow-up contact will be recorded. The source documents will be the subject diary cards, and the clinical records, from which AEs (as described above) will be transcribed to the CRF.

Any unresolved AE will be followed until its resolution or until the 24 month follow-up telephone contact, whichever occurs first.

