13.2 Variables and Timepoints of Measurement

13.2.1 Safety Variables

In-clinic safety evaluation on Days 0, 3, 7, 42, 180, and 360 will be graded for severity and relationship to the study agents and will include:

- a) Rates of SAEs and their relationship to device placement, through 2 years of long-term follow-up.
- b) Rates of local or systemic solicited AEs and their categories (mild, moderate and severe), through Day 360 ± 28 days.
- c) Rates of reported unsolicited AEs, through Day 360 ± 28 days.
- d) Hematologic and biochemical toxicity evaluation following device placement.

Osteogenicity will be evaluated using radiographs and CT scans obtained from participants on Day 0 (baseline, pre-implantation), Day 42 (± 7), 6 weeks after device placement), and Day 180 (± 14) 6 months after device placement).

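### SAE rates are defined through 2 years but the last scheduled analysis follows Day 360 data, and the unsolicited AE rate stops at Day 360 although those events are collected to the 2-year contact

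*Protocol*

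**What the plan says.** Protocol 6.1: "The primary objective is to evaluate the safety of the B-247 Cranial Bone Graft Implant". No duration is attached to the objective.

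**Collection.** Section 7.1 states that "unsolicited adverse events will be collected immediately following surgical device placement through two years via telephone contacts and at clinic visits". Section 10.1 documents AEs through Contact 3. Section 11.1.2 provides Diary Card #5 for unsolicited AEs and SAEs from Day 360 to Day 720. Section 11.1.3 covers all AEs and SAEs "until the follow-up assessment at Contact #3 (Day 720) will be recorded".

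**Variables.** Section 13.2.1(a): "Rates of SAEs and their relationship to device placement, through 2 years of long-term follow-up". Section 13.2.1(c): "Rates of reported unsolicited AEs, through Day 360 ± 28 days". Item (b), on solicited AEs, has the same Day 360 ± 28 limit.

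**Analysis times.** Section 13.1.1 places full statistical analyses "after all Day 180 data is received in-house, and again after all Day 360 data is received in -house". No analysis after the 2-year contact is named anywhere in the protocol.

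**The 2-year call.** The telephone follow-up paragraph in 9.1 has staff "collect information on ongoing, previously recorded adverse events and new or ongoing SAEs", and 7.1 says the call is to "document the occurrence of SAEs and the resolution of AEs ongoing at the one-year visit". The Contact 3 checklist in 9.1 is wider and has staff record AEs as well as SAEs.

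**The concern.** The protocol sets three things separately: how long events are collected, how long each rate runs, and when the data are analysed. They do not agree. For SAEs, collection and the rate both run to 2 years, but the last analysis is triggered by Day 360 data. For non-serious unsolicited AEs, collection runs to 2 years while the rate stops at about one year.

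This bears on the primary objective. Section 5.5 says there is no previous human experience with this plasmid approach, so late events are part of what the study is meant to learn. If the text is followed literally, the 2-year SAE rate has no reporting point. Non-serious events on Diary Card #5 would be gathered without a stated place in the rates of 13.2.1.

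**Working it through.** **1. The plan's own safety figure.** Section 13.1 gives a 90% chance of at least 1 SAE in 10 subjects at a true rate of 21%. Check: 1 − 0.79^10 = 90.5%. It reproduces. The section does not say over what period the 21% applies.

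**2. Windows side by side.**

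| Item | Collected to | Rate defined to | Last scheduled analysis |
|---|---|---|---|
| SAEs | 2 years (7.1, 10.1, 11.1.3) | 2 years (13.2.1(a)) | Day 360 data (13.1.1) |
| Unsolicited non-serious AEs | 2 years (7.1, 10.1, 11.1.2, 11.1.3) | Day 360 ± 28 (13.2.1(c)) | Day 360 data |
| Solicited AEs | 1 year on diary cards plus the 2-year call (Synopsis), or 2 years (7.1) | Day 360 ± 28 (13.2.1(b)) | Day 360 data |

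The second analysis starts once the last subject's Day 360 data are in. Early enrollees may have longer follow-up by then, but the last subject cannot have reached 2 years. The row for SAEs therefore cannot be completed for all 12.

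**3. Share of follow-up beyond the unsolicited AE rate.**
- From Day 360: (720 − 360)/720 = 50%.
- From the end of the window, Day 388: (720 − 388)/720 = 332/720 = 46%.
- With Day 730 as the contact (9.1 and 10.1): 370/730 = 51% and 342/730 = 47%.

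**4. Illustration only.** Assume a constant hazard, independent subjects, complete follow-up, and exactly one year of data per subject at the Day 360 analysis. None of this is given in the protocol. If the 2-year risk is p, the 1-year risk is 1 − √(1 − p). With n = 12, the chance that at least one subject has an event is 1 − (1 − p)^12 on 2-year data and 1 − (1 − p)^6 on 1-year data.

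| Assumed 2-year risk | 2-year data | 1-year data |
|---|---|---|
| 5% | 46.0% | 26.5% |
| 10% | 71.8% | 46.9% |
| 20% | 93.1% | 73.8% |

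On the same assumptions, if the 21% in 13.1 is read as a 2-year risk, the plan's 90.5% for n = 10 becomes 1 − 0.79^5 = 69.2% on one-year data.

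**The case against.** The strongest reply is that timing of a long-term follow-up table is SAP matter, that naming two full analyses does not forbid a third, and that 13.1.1 makes the statistician responsible for all safety data. It is also coherent to estimate non-serious AE rates over the year of clinic visits and SAE rates over two years, since the Synopsis separates the final clinic visit at 1 year from follow-up through 2 years. Part of this stands: a Day 360 window for non-serious AEs is a permissible choice, and a rate with a shorter window is not thereby an understated one. It does not remove the conflict over SAEs, because the protocol itself sets both the 2-year variable and the two analysis times. Nor does it say what becomes of the non-serious AEs collected after Day 360. The scheduled Safety Review Committee meetings do not fill the gap, since 14.2 ties them to active enrollment and follow-up to Day 42.

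A reader might infer more than the text supports:
- *That the second year never reaches the safety result.* Section 13.2.1(a) plainly intends year-2 SAEs to be in it. The Synopsis incidence endpoints and the 13.3.1 tabulations also have no Day 360 limit.
- *That the 2-year call does not ask about new non-serious AEs.* The Contact 3 checklist, the Schedule of Evaluations and 11.1.3 all include them. Only the narrative sentences in 7.1 and 9.1 are narrower, which is an inconsistency of wording.
- *That the primary objective is answered for half its duration.* Section 6.1 states no duration.

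**Conclusion.** The point holds as a conflict between rules that the protocol itself fixes. The 2-year SAE rate in 13.2.1(a) has no scheduled analysis able to produce it. Section 13.2.1(c) leaves 46% to 50% of a 720-day follow-up outside the unsolicited AE rate, while events from that period are still collected. Both conclusions rest on the stated dates alone and need no statistical assumption.

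The probabilities in the illustration are not estimates of what would be missed. They depend on an assumed incidence and a constant hazard, and early events may dominate after a single surgical implant. No sample-size figure changes. The point should be corrected because it touches the primary objective and is cheap to settle.

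**What to change.** 1. In 13.1.1, add a final safety analysis after all Contact 3 data are received, and state that it reports the 2-year SAE rate.
2. In 13.2.1(c), extend the window to Contact 3 and tabulate year 1 and year 2 separately. At the least, state that non-serious AEs after Day 360 are listed in that final analysis.
3. Reconcile 13.2.1(b) with the two solicited AE periods (1 year on diary cards in the Synopsis, 2 years in 7.1).
4. Use one day for Contact 3: it is Day 720 in Section 3, 11.1.2 and 11.1.3, and Day 730 in 9.1 and 10.1.
5. Align the narrower sentences on the 2-year call in 7.1 and 9.1 with the Contact 3 checklist and 11.1.3.

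The cost is protocol wording, one extra set of tables for 12 subjects, and a final report that waits for the 2-year contact. No visit or procedure is added, since the protocol already requires these data.

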13.2 Variables and Timepoints of Measurement

13.2.1 Safety Variables

In-clinic safety evaluation on Days 0, 3, 7, 42, 180, and 360 will be graded for severity and relationship to the study agents and will include:

- a) Rates of SAEs and their relationship to device placement, through 2 years of long-term follow-up.
- b) Rates of local or systemic solicited AEs and their categories (mild, moderate and severe), through Day 360 ± 28 days.
- c) Rates of reported unsolicited AEs, through Day 360 ± 28 days.
- d) Hematologic and biochemical toxicity evaluation following device placement.

Osteogenicity will be evaluated using radiographs and CT scans obtained from participants on Day 0 (baseline, pre-implantation), Day 42 (± 7), 6 weeks after device placement), and Day 180 (± 14) 6 months after device placement).

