2. PROTOCOL SYNOPSIS

Protocol Title: A Phase I/IIa safety and efficacy study of a synthetic bioactive bone graft device for cranial bone regeneration in adults

Protocol Number:

Investigational Product: Plasmid DNA (pln.247-pBI, 200 µg/ml) for transient expression of human perlecan domain 1 with 100 µg/ml rhBMP-2 in a gelatin/ tricalcium phosphate scaffold for cranial bone regeneration (B-247 Cranial Bone Graft Implant).

Placebo (Vehicle): none

Sponsor: Agenta Biotechnologies, Inc.
[name]
[name]

Study Site: UAB Health System
Birmingham, Alabama

Investigator: [name].
Division of Neurological Surgery
[name]
[name]
[name]

Name of IRB: Western IRB
[name]
[name]

Proposed Start Date: Quarter 3, 2013

Study Duration: For each subject, from day of device implant to final clinic visit at 1 year, with follow-up through 2 years.

Study Objectives: The objectives of this study are as follows:

- To evaluate the safety of a B-247 Cranial Bone Graft Implant
- To evaluate bone regeneration associated with placement of the B-247 Cranial Bone Graft Implant.

Study Design: Single center, single dose study unblinded safety and efficacy trial.

Number of Subjects: 12 total subjects, one group

	Number of Subjects	Dose Level
Group 1	12	200 µg/ml pln.247-pBI + 100 µg/ml rhBMP-2

Study Population: Trauma and Surgical Craniotomy patients, male, 19 to 59 years of age

Route of Administration: Localized direct surgical placement of investigational product in cranial defect

Dose and Schedule: Subjects will receive investigational product at time of surgery.

General Study Conduct: Subjects who consent to participate in the trial will be screened for eligibility immediately. Baseline data, including pre-operative CT images, will be made prior to surgery. Subjects and investigators will be unblinded to the treatment.

- 1) in-hospital surveillance for the first 7 days after administration of investigational product;
- 2) in-clinic physical assessments on Days 0, 3, 7, 42, 180, and 360;
- 3) lab testing at Days 0, 7 and 42;
- 4) solicited adverse events (AEs) recorded on diary cards for 1 years after administration; and during phone contact at 2 yr. follow-up.
- 5) collection of unsolicited adverse events during active follow up to Day 360 and during phone contact at 2 year follow-up.

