11.1.2 Solicited Local and Systemic Events

All subjects will be given diary cards that are to be filled out for the purposes of recording any changes in health status after device administration.

- Diary Card #1 will be used to record all local and systemic events, as well as any other AEs that represent a change in the health status of the subject, from device placement through Visit 3 (Day 7).
- Diary Card #2 will be used to record unsolicited adverse events and SAEs through Visit 4 (Day 42).
- Diary Card #3 will be used to record unsolicited adverse events and SAEs after Visit 4 (Day 42) through Visit 5 (Day 180).
- Diary Card #4 will be used to record unsolicited adverse events and SAEs after Visit 5 (Day 180) through Visit 6 (Day 360).
- Diary Card #5 will be used to record unsolicited adverse events and SAEs after Visit 5 (Day 360) through Contact #3 (Day 720).

The diary cards will be considered the source document and will be transcribed into the case report form (CRF) by study site personnel. If the diary card is lost, this will be documented in the CRF, and the limited information collected during the clinic visit will serve as the source document. All other data points will be noted with "ND" (not determined).

For the purpose of collecting solicited local and systemic events, the following procedures will be implemented:

1. Study participants will be supplied with a digital thermometer on day 7 and shown how to use it to measure their oral temperature for weeks 1-6 following administration of the study product.
2. Participants will be asked to observe for AEs daily during the first 6 weeks post-implantation period. This includes systemic events including fever, chills, nausea/vomiting, weakness, muscle pain, and headache.
3. Diary Card #1 will be distributed during Visit 1 (Day 0) and collected during Visit 3 (Day 7). Diary Card #2 will be distributed during Visit 3 (Day 7) and collected during Visit 4 (Day 42). Diary Card #3 will be distributed during Visit 4 (Day 42) and collected during Visit 5 (Day 180). Diary Card #4 will be distributed during Visit 5 (Day 180) and collected during Visit 6 (Day 360). Diary Card #5 will be distributed during Visit 6 (Day 360) and collected by mail at Contact #3 (Day 720). Subjects will be asked

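### The solicited-AE collection period is stated in four incompatible ways, and the diary cards do not support a solicited-AE rate through Day 360

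*Protocol*

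**What the plan says.** The variable is defined in Protocol section 13.2.1(b): "Rates of local or systemic solicited AEs and their categories (mild, moderate and severe), through Day 360 ± 28 days".

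The period over which solicited events are collected is given differently in four places:

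- **Section 11.1.2, card descriptions.** Card #1 (placement to Day 7) is the only card assigned local and systemic events. For the next card the text reads: "Diary Card #2 will be used to record unsolicited adverse events and SAEs through Visit 4 (Day 42". Cards #3, #4 and #5 have the same content, ending at Days 180, 360 and 720.
- **Section 11.1.2, item 2.** Under procedures meant for solicited events: "Participants will be asked to observe for AEs daily during the first 6 weeks post-implantation period". The symptoms then named (fever, chills, headache and others) are all systemic.
- **Synopsis, General Study Conduct.** "solicited adverse events (AEs) recorded on diary cards for 1 years after administration", and also at the 2-year telephone contact.
- **Section 7.1.** "Each participant will be requested to record solicited AEs daily for 2 years after their device placement using study diary cards".

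Three related texts also disagree:

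- **Temperature.** Section 11.1.2 item 1 says "Study participants will be supplied with a digital thermometer on day 7", for readings covering weeks 1 to 6.
- **Unsolicited AEs.** Section 11.1.3 collects them to Day 720, and section 13.2.1(c) reports them to Day 360. For the 2-year call, the narrative in section 9.1 has staff "collect information on ongoing, previously recorded adverse events and new or ongoing SAEs", while the Contact 3 checklist below it lists AEs and SAEs without that limit.
- **SAEs.** Section 13.2.1(a) requires rates through 2 years. Section 13.1.1 names a full analysis after Day 180 "and again after all Day 360 data is received", and no later one.

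**The concern.** Safety is the primary objective (section 6.1), and section 7.1 names solicited and unsolicited events separately among the components of the overall safety assessment. A solicited rate has meaning only if subjects are prompted for the same listed events throughout the period it covers. If prompting stops at Day 7 or week 6 while the rate runs to Day 360, one proportion combines two methods of ascertainment. With 12 subjects and no control arm, one missed subject moves a proportion by 1/12 = 8.3 percentage points.

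This is not a detail that an analysis plan can settle later. What subjects are asked, on which card and for how long is fixed by the protocol, and prompted data that were never collected cannot be recovered at analysis.

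**Working it through.** The plan states no figure to reproduce here, so the check sets the passages side by side.

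**Step 1. Share of the 360-day reporting period with solicited collection (collection days / 360).**

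| Source | Collection period | Share |
|---|---|---|
| 11.1.2, Card #1 | 7 days | 7/360 = 1.9% |
| 11.1.2, item 2 | 6 weeks (42 days) | 42/360 = 11.7% |
| Synopsis | 1 year | 360/360 = 100% |
| 7.1 | 2 years (720 days) | 720/360 = 200% |

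Only the synopsis period matches 13.2.1(b), and the descriptions of Cards #2 to #4 do not implement it. Item 2 also conflicts with the label of Card #2: subjects are to look daily for named symptoms to week 6 while holding a card described as unsolicited.

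**Step 2. What ascertainment remains after prompting ends.** Section 11.1.3 requires AEs to be actively surveyed at every visit and telephone contact, and section 11.1.2 has staff review the diary card at each visit. After Day 42 the in-clinic visits are at Days 180 and 360, so the intervals are 180 − 42 = 138 days and 360 − 180 = 180 days. No symptom checklist is stated for those visits.

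**Step 3. Could the rate be understated, and by how much?** The documents give no event rates and no capture rates, so the following is an illustration on assumed values. Let pe be the probability of a solicited-type event in Days 0-7, pl the probability in Days 8-360, and c the share of later events that is recorded.

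- Reported proportion = 1 − (1 − pe)(1 − c·pl)
- Chance of at least one recorded late event in 12 subjects = 1 − (1 − c·pl)^12

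With pe = 10% and pl = 20%:

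| c | Reported proportion | At least one late event in 12 |
|---|---|---|
| 1 | 1 − 0.90 × 0.80 = 28.0% | 93% |
| 0.75 | 1 − 0.90 × 0.85 = 23.5% | 86% |
| 0.50 | 1 − 0.90 × 0.90 = 19.0% | 72% |
| 0.25 | 1 − 0.90 × 0.95 = 14.5% | 46% |

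Other assumed values give other losses. At c = 0.25, pe = 30% with pl = 10% takes 37.0% to 31.8%, and pe = 10% with pl = 30% takes 37.0% to 16.7%. At c = 1 nothing is lost. The result depends wholly on c and pl, neither of which the protocol supplies.

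**Step 4. Related time points.** Unsolicited AEs are collected to Day 720 and reported to Day 360. SAE rates are required to 2 years, while the named analyses follow Days 180 and 360. Both pairs are mismatched on the text alone.

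**The case against.** The strongest reply is that later events are neither lost nor left to chance. Section 11.1.3 surveys AEs actively at every contact, item 2 of section 11.1.2 prompts for named systemic symptoms to week 6, and staff review the diaries. The synopsis endpoints and the tabulations in section 13.3.1 count adverse events without separating solicited from unsolicited, and the stopping rules in section 14.3 do not use the distinction. A recorded event is therefore counted under either label, in a small descriptive study.

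Much of this stands, and it rules out several stronger readings:

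- **That events after Day 7 appear only if volunteered, so about 98% of the window is uncovered.** Sections 11.1.2 and 11.1.3 say otherwise. The shares in Step 1 measure calendar time, not missed events.
- **That the rate is understated.** Under-recording of mild, transient events between distant visits is plausible, but it is not shown.
- **That the 2-year call asks only for SAEs and known AEs.** One paragraph of section 9.1, and section 7.1, read that way. The Contact 3 checklist, the Schedule of Evaluations and synopsis item 5 collect AEs more broadly. This is a conflict of wording.
- **That week-1 temperature goes unmeasured.** The synopsis plans in-hospital surveillance for 7 days, and vital signs are scheduled on Days 0, 3 and 7. Only subject-held readings are clearly absent. The telephone contacts on Days 1 and 2 and the Day 3 appointment in section 9.1 sit badly with an inpatient week, so this too needs reconciling.
- **That year-2 safety data will go unanalysed.** Section 13.1.1 does not call the Day 360 analysis the last. It only fails to name a time point that serves the 2-year variable.

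The reply does not remove the core. Section 13.2.1(b) still sets up a separate solicited variable that the cards, as described, cannot deliver.

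**Conclusion.** The point holds as an internal contradiction. Four solicited-AE periods are stated (7 days, 6 weeks, 1 year, 2 years), and the card descriptions support only the shortest, against a reporting period of 360 days. Followed as written, the rate through Day 360 would mix daily prompted recording with general questioning at intervals of up to about six months. It may be understated. The size is not computable from the documents, and the figures in Step 3 rest on assumed event and capture rates. The contradiction itself needs no assumption.

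The protocol should be corrected, because a component of the primary safety assessment is affected and the collection rules cannot be repaired after the fact. Nothing here implies that overall AE recording fails. The thermometer, unsolicited-AE and 2-year SAE mismatches are smaller and belong in the same correction.

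**What to change.** Reconcile section 11.1.2, section 7.1, the synopsis and section 13.2.1(b) to one solicited period, and make the cards match it. Either route works:

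1. **Shorten the variable.** Limit solicited AEs to the period in which the cards prompt for listed events, for example Day 0-42 with Card #2 carrying the solicited list, and report later events as unsolicited. This uses the 6-week procedure already written.
2. **Extend the prompting.** Put the solicited list on Cards #2 to #4 and keep Day 360, on which the synopsis and section 13.2.1(b) already agree.

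Under either route, name the solicited local events, since item 2 lists only systemic ones.

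In the same amendment:

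- Reconcile the Day 7 thermometer issue with the weeks 1 to 6 temperature recording and with the inpatient and telephone arrangements for week 1.
- Give unsolicited AEs one end date across sections 11.1.3 and 13.2.1(c) and the conflicting Contact 3 texts.
- State a safety analysis after Contact 3, so that the 2-year SAE rates in section 13.2.1(a) have a matching time point in section 13.1.1.

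The cost is card redesign and protocol wording, with no new visits. The first route gives up the claim to a full year of solicited AEs; the second asks more of subjects and depends on diary compliance over a year.
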